BACtrack Keychain: https://www.bactrack.com/products/bactrack-keychain- breathalyzer?&mkwid=Ch2zPSsL&pcrid=102311672917&pkw=bactrack%20keychain&pmt=e&pdv=c&ring-central=googleppc&gclid=CjwKEAiAs_PCBRD5nlun9cyu01kSJAA-WDruugi8lvC2_Z7nN_Mz40Fd2MYTiexYL2MMobRXXZfIRoCLLvw_wcB

2. Group Modifications:

Because there are no trial arms in this study, all participants will complete the same study activities, and there will be no group modifications necessary. Because of the limited availability of the Bactrack Skyn measurement tool, only a portion of our participants will receive this device depending on availability of the device.

3. Method for Assigning Subjects to Groups:

There will be no randomization for this study. All participants will receive the same study protocol. Except a selection of participants will be instructed to wear the Bactrack skin wristband for the duration of the study. This will not effect any other aspect of the study protocol.

4. Administration of Surveys and/or Process:

Interested participants will call the study hotline where an IRB-approved research assistant or project manager, will answer any questions, administer the study screening and go over the written informed consent. There will be an optional in person study visit for the participant to come in and review study procedures, and sign written informed consent, in person. At the study visit, which occurs at a predetermined time, the participant will first sign written informed consent to participate. They will then take an initial survey, with questions related to their past alcohol use and habits including Driving History and Experience Questionnaire DHEQ1, Drinking and Driving Questionnaire. Participants will also take the Decision making survey, which includes The Barratt Impulsiveness Scale, and the Delayed discounting questionnaire. Some participants will then be instructed to wear the BACtrack skyn wrist device. Participants will then receive three doses of vodka mixed with juice based on their gender and weight designed to reach a peak blood alcohol level of .08 g/dL. After each dose their Breath Alcohol Content (BrAC) will be measured using the three smartphone breathalyzers and the intoxilyzer, measured in a random order. After each breathalyzer measurement, participants will receive the Self-Report of Intoxication Survey, which will include Perceived Driver Fitness and Perceived intoxication and BAC estimation, which are measured using a visual analogue scale.

Besides a preliminary study visit for participants to consent to the study and complete the eligibility survey, all research activities will take place in one of the four CTRC study sites and will occur in a study session of approximately six hours in length with up to four participants at each session for a total of five study sessions. Participants will be separated by curtains and fill out individual paper surveys on paper sheets in order to maintain confidentiality.

Data collection will include contact information, medical history, and history of alcohol use, various measurements of Breath Alcohol Content (BrAC), as well as survey data from the self-reported intoxication survey. The informed consent process during study enrollment will describe all of these aspects of data collection.

5. Data Management:

Paper forms will be used to collect data and a research assistant will create and maintain the research database. All source documents will be identified by study identification (ID) number, and the key to that ID number will be kept in a locked file cabinet. All personally identifiable information also will be kept separately in a locked file cabinet. No results will be reported in a personally identifiable manner. All tracking system data and research database information will be password-protected with several levels of protection: first, a password will be required to access the computer of the user who has access to the

6. Statistical Analysis Plan:

Primary outcome: Interclass correlation coefficient between smartphone breathalyzer and wearable device readings and the police breathalyzer readings. (See: https://en.wikipedia.org/wiki/Intraclass_correlation).

Secondary outcomes: mean relative differences in breathalyzer and wearable device readings relative to the police breathalyzer with standard deviations. These will be calculated for all measurements and by specific timepoints.

Other secondary analyses: We will conduct descriptive analyses of the association between self-reported measures of intoxication, predicted blood alcohol content, driving fitness, and willingness to drive with measured breath alcohol content by device. We will also explore the effect modification of these by self-reported measures of impulsivity and delay discounting.

RISK/BENEFIT ASSESSMENT:

1. Risks:

There is some risk that subjects will be identified as participants in the study and that the confidential information provided regarding psychiatric and substance use history will be inadvertently disclosed without the subjects' permission. Urine pregnancy testing is performed for all women of reproductive potential, prior to alcohol administration, to avoid the potential for adverse fetal effects of alcohol. These procedures should add no additional risks beyond the minimal risks normally associated with them.Over a period of 120 minutes, participants will be given three doses of alcohol, which will result in a BrAC of 1.01-1.02g/dL. This amount of alcohol is equivalent to 4-5 standard drinks, an amount that these moderate-drinking subjects have ingested previously. Although the amount of alcohol available to them will produce only moderate blood alcohol levels, subjects could feel intoxicated or react negatively to the alcohol, such as nausea or dehydration. Engaging in any dangerous activities during this period would increase risk of self-harm. Precautions to minimize these risks are discussed below.

After consuming alcohol, participants may be unsafe to operate a vehicle. This risk will be mitigated by providing participants transportation home with either a septa token or rideshare credits for uber of up to \$30, depending on their location. Study activities will be performed in a special clinical research room located in a hospital setting in close proximity to an inpatient care. Nursing and medical personnel will be available to assist in the care of the subject if any adverse event occurs. Participants' breath alcohol concentration (BrAC) and their general condition will be monitored during all aspects of the procedure. The bar-lab will be located in a safe and secure area in in a hospital where medically trained staff will be onsite and there will be ready access to emergency care should it be necessary. All subjects will remain in the test area until their BrAC will be below 0.03 g/dL. All study activities will occur in the afternoon, no earlier than 11am, to minimize nausea and vomiting that could occur with morning alcohol consumption. A meal will be provided.

Rating Scales and Questionnaires. To avoid breach of confidentiality, subjects' names will appear only on a consent form, a telephone screening form and a "key" form kept in a locked cabinet. All forms that contain identifying information will be kept double locked (i.e., in a locked cabinet, in a locked room) to maintain their security. All study data forms will contain only the subject's unique study identification number, using a reference system maintained by the study staff. Completed study forms will be kept in a locked cabinet, the key to which will be available only to the PI and staff working on this study. Subject visits will be scheduled and no information about the subject will be provided to anyone (except in emergencies as defined above) in person or by telephone.

All paper research records will be stored in locked cabinets and only the investigators and only IRB approved study will have access to those records.

2. Benefits:

There are no direct benefits to participation. Participants are contributing to preparation of a larger study, which in turn may have benefits to society in general. Given that anecdotal research shows variation in Breathalyzer readings, understanding the validity of smartphone paired breathalyzers has potential to benefit society in general.

3. Subject Privacy:

Participants will be screened for eligibility over the telephone with a trained research team member in a private office. The participant will review the paper consent form in a private room on the day of the study visit. The participant will have a private room in the research lab during the study visit.

4. Subject Confidentiality:

Participants who have seen recruitment material will call a study line in order to sign up for the study. At this pre-screening phone call, the research project manager will briefly go over study procedures. If the participant is interested, they will be complete a brief (less than ten minute) screening over the phone to determine eligibility. Participants may be asked to meet with the study staff prior to scheduling their study visit to determine eligibility. At the study visit, eligible participants will sign written informed consent, and be administered the study protocol; all study documents will be de-identified after all contact has been made. Participant information will be stored in a locked filing cabinet only accessible by the research assistants, PI, and project manager. Personal information will not be stored with study data and will be destroyed after data collection.

How will confidentiality of data be maintained? Check all that apply.

 \boxtimes Paper-based records will be kept in a secure location and only be accessible to personnel involved in the study.

Computer-based files will only be made available to personnel involved in the study through the use of access privileges and passwords.

Prior to access to any study-related information, personnel will be required to sign statements agreeing to protect the security and confidentiality of identifiable information.

Whenever feasible, identifiers will be removed from study-related information.

A Certificate of Confidentiality will be obtained, because the research could place the subject at risk of criminal or civil liability or cause damage to the subject's financial standing, employability, or liability.

 \boxtimes A waiver of documentation of consent is being requested, because the only link between the subject and the study would be the consent document and the primary risk is a breach of confidentiality. (This is not an option for FDA-regulated research.)

Precautions are in place to ensure the data is secure by using passwords and encryption, because the research involves web-based surveys.

Audio and/or video recordings will be transcribed and then destroyed to eliminate audible identification of subjects.

Other (specify):

We will require a waiver of consent written consent in order to administer the screening survey over the phone because it is not feasible for each participant to be required to come in, in order to answer questions in the screening survey. Before the screening survey is administered, participants will be prompted to provide verbal consent (attached to this protocol) over the phone, using the verbal consent script that is attached to this protocol. Once a participant is screened, using the screener, and has set up a study session, participants will signed written informed consent at the beginning of their study visit prior to any other activities being completed.

5. Protected Health Information

- Name
- Street address, city, county, precinct, zip code, and equivalent geocodes
- All elements of dates (except year) for dates directly related to an individual and all ages over 89
- Telephone and fax number
- Electronic mail addresses

6. Compensation:

Each subject will receive a \$100 cash card as an incentive for completing the 6 hour study session. This cashcard will work through the Greenphire clincard system (SOP attached to this submission). Information about the greenphire system will be provided in the consent document for the participant. Information, including social security number, will be collected from the participant at the intake phone call in order to set up an online account that the participant will be able to access. Participants will be reimbursed for travel and ensured a ride home by receiving either a septa token or up to \$30 in rideshare credits from Uber.

7. Investigator's Risk/Benefit Assessment:

In general the benefits outweigh the risks in this study. Participants will receive information on alcohol consumption and health. Participants are also contributing to preparation of a larger study, which in turn may have benefits to society in general. Although there are some risks involved in participating in this study, as mentioned above, these can be minimized to ensure that the potential benefits exceed the potential risks, so that the risk/benefit ratio is favorable.

INFORMED CONSENT:

1. Consent Process:

Participants will respond to recruitment material by calling the study hotline. After calling the study hotline, participants will be screened for eligibility and will schedule a visit. At the study visit, participants will sign written informed consent. Consent will be obtained by explaining the study objectives, procedures, and potential risks to subjects verbally and in writing at a pre-screening and / or screening visit. Subjects will be given an opportunity to ask questions and will be provided with complete and accurate answers to any questions they may have. Written documentation of this process will be obtained using the IRB-approved consent form. Subjects are given a signed copy of the consent form for his or her reference.

2. Waiver of Informed Consent:

This research in general involves minimal risks to the participants because the benefits outweigh the risks in this study. Specifically the waiver of consent only applies to administration of the screening survey, and completing this survey involves minimal risk to participants, such as there is some risk that confidential information provided regarding psychiatric and substance use history will be inadvertently disclosed without the subjects' permission. Methods outlined elsewhere in this

protocol will be in place to protect participant information to minimize this risk. Also the benefits for allowing participants to take screening over the phone and not having to come in for two study visits outweighs this risk.

It is not always feasible for participants to schedule a separate study visit to answer a brief screening survey. In order to accommodate participants who cannot schedule a separate study visit, we are requesting a waiver of written informed consent only to administer the screening survey over the phone. Allowing this step in the process to be completed over the phone will make the study more feasible to be completed by participants.

Once a participant is screened, using the screener, and has set up a study session, participants will sign written informed consent at the beginning of their study visit prior to any other activities being completed.

RESOURCES NECESSARY FOR HUMAN RESEARCH PROTECTION:

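### Social security numbers are collected by phone for payment, before written consent and outside the stated consent waiver

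*Combined protocol and SAP*

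**What the plan says.** All references are to the final protocol.

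- **Risk/Benefit Assessment, 6. Compensation.** On timing: "Information, including social security number, will be collected from the participant at the intake phone call in order to set up an online account". The same section says that "Information about the greenphire system will be provided in the consent document for the participant". The $100 card is paid "as an incentive for completing the 6 hour study session".
- **Informed Consent, 2. Waiver of Informed Consent.** The scope is stated twice: "Specifically the waiver of consent only applies to administration of the screening survey", and again, "we are requesting a waiver of written informed consent only to administer the screening survey over the phone". After screening and scheduling, "participants will sign written informed consent at the beginning of their study visit prior to any other activities being completed".
- **Informed Consent, 1. Consent Process.** On the order of steps: "After calling the study hotline, participants will be screened for eligibility and will schedule a visit". Written consent follows at the visit.
- **Risk/Benefit Assessment, 3. Subject Privacy.** "The participant will review the paper consent form in a private room on the day of the study visit".
- **Risk/Benefit Assessment, 4. Subject Confidentiality.** Verbal consent is taken by phone ahead of the screening survey, from a script attached to the protocol. The ground ticked for waiving documentation of consent is that the consent form would be the only thing linking the person to the study, with breach of confidentiality as the main risk.
- **Risk/Benefit Assessment, 5. Protected Health Information.** The list gives name, address, dates, telephone and fax, and e-mail. It does not give the social security number.

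**The concern.** Opening a payment account is a different task from administering a screening survey, and the survey is the only activity for which written consent is waived. As written, a highly sensitive identifier is requested from people whose only documented agreement is verbal and tied to that survey.

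What is at stake is participant protection. The Risks section names inadvertent disclosure of confidential information as a risk of the study. The waiver section argues minimal risk by reference to psychiatric and substance-use history, and does not weigh the social security number. The number also identifies a person in its own right, which fits poorly with a waiver resting on the consent form being the sole link. A person who gives it and then never starts has handed it over for a payment that will not fall due.

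**Working it through.** No arithmetic applies and the plan gives no figure to reproduce. The check sets the sections side by side and follows one person through them.

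1. **Call and screening.** The person rings the hotline, gives verbal consent to the survey, is screened and books a visit (Consent Process; Subject Confidentiality).
2. **Social security number.** It is collected at the intake phone call (Compensation). That call is not defined, but the final protocol describes no phone contact after written consent: the hotline call, the pre-screening call and the phone screening all come before the study visit. I take the intake call to be one of these.
3. **Written consent.** It is signed at the start of the study visit. Methods, 4. Administration of Surveys and/or Process also allows signature at an optional earlier in-person visit. That visit is optional, and the waiver is justified by people who cannot make a separate visit, so it cannot be the ordinary route.
4. **Scope of the waiver.** It covers the phone survey alone. Subject Confidentiality describes the screening as a brief exercise to determine eligibility. Payment details play no part in eligibility.
5. **Explanation of the payment system.** It is in the consent document, and the paper form is reviewed on the day of the visit.

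Step 2 comes before step 3 on the ordinary route, and step 4 does not cover it. The groups then separate as follows:

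| Group | Written consent when the number is given | Written consent later |
|---|---|---|
| Enrolled after phone scheduling only | No | Yes, at the visit |
| Fail breath, pregnancy, medical or suicidality checks on the day | No | Yes: Methods, 3. Study Visit puts signature ahead of these checks |
| Scheduled but do not attend, or decline to sign | No | Never |

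Someone who uses the optional earlier visit may have signed first. The text does not say whether the phone collection comes before or after that visit.

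The card rewards completion of the session, and nothing in Compensation explains why the number is needed before attendance.

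**The case against.** **Consent is discussed by phone.** Methods, 2. Phone Screening and 4. Administration of Surveys and/or Process have staff go over informed consent during the call, so some callers may hear about the payment system first. This softens the harm. It is not signed consent, and the waiver replaces a signature only for the survey.

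**Unseen attachments.** The verbal script and the payment procedure are attached but not available here, and the script might mention the number. That cannot be excluded, but the protocol text ties verbal consent to the survey, and the waiver's limiting word would still need changing.

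**Safeguards.** Identifying forms are double locked, and personal information is kept apart from study data and destroyed after data collection. These reduce the chance of disclosure. They do not bring payment data within the waiver, and no earlier deletion is stated for people who never start.

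**Stronger readings that a reader might infer, and that the documents do not support:**

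- *The protocol says it is not entitled to the number at that point.* No section says so. What it does is limit the waiver and place the signature later.
- *The two rules are flatly impossible to follow together, because consent must come before every other activity.* That phrase is attached to the start of the study visit and can be read as governing visit activities only. The conflict rests on the scope of the waiver, which is explicit.
- *People who fail the checks on the day gave only verbal consent.* They sign on arrival, before the checks.
- *A count of affected non-starters can be given.* It would need a non-attendance rate, and none is stated.

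**Conclusion.** The point holds as an inconsistency within the current text with a practical consequence: followed literally, staff take social security numbers by phone before written consent, for a purpose that the waiver does not cover. It applies to everyone on the ordinary phone-scheduled route. For those who later sign, the defect is one of timing. For scheduled people who never attend or who decline to sign, written consent never comes. The size of that last group is unknown, as is whether the number is asked of every caller or only of those found eligible; on either reading, scheduled people who do not attend are included.

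The conclusion assumes that the intake phone call takes place before the visit and that the unseen script does not extend the waiver. The missing entry in the Protected Health Information list is a separate, smaller gap that depends on neither. Sample size, outcomes and analysis are untouched. The change is worth making because it is cheap and bears on a risk that the protocol itself names.

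**What to change.** In Compensation, replace collection at the intake phone call with collection at the study visit, or at the optional earlier visit, after written informed consent has been signed. Add the social security number to the Protected Health Information list. Waiting until the eligibility checks are also passed would be a further preference; resolving the conflict does not require it.

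The cost is a minor amendment and a few minutes of card set-up on site instead of beforehand. If there is a reason to keep phone collection, the text could instead be reconciled by extending the waiver, the verbal script and the identifier list to name the number expressly. That route keeps the exposure of people who never start, so the first is preferable.
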